### **8.2.2 Laboratory Evaluations**

At the time points described in Section 8.1, blood will be collected for analysis of creatinine, ionized or corrected calcium, Vitamin D (D2+D3), iPTH, CTX, P1NP, OCN, RANKL, OPG, IL-6, IL-7, and TNF- $\alpha$ . Urine will also be collected for analysis of DPD, creatinine, and albumin. Analysis will be performed as described in Section 8.3.

For female patients > 10 years of age, a urine or serum pregnancy test will be performed at Screening and within 72 hours before administration of each dose of pamidronate for subjects randomized to the Pamidronate Group.

### **8.2.3 Medical Examination and Anthropometrics**

A physical examination will be performed by a trained pediatric provider at study screen/entry and at the day 360 visit per section 8.1. Height will be recorded at study entry and on day 360. Weight will be recorded at study screening/entry and on days 90, 180, 270 and 360. Tanner staging of pubertal development, including breast and pubic hair development in girls (52), and pubic hair development in boys (53) will be performed at each physical exam. Height will be measured standing without shoes with a wall-mounted stadiometer. Weight will be measured with subject in light clothing or dressing gown with shoes removed. These measurements will be used to calculate BMI as weight (kg) divided by height (m^2).

### **8.2.4 DXA and pQCT**

Subjects will have DXA scans of L1-L4 and total body with body composition performed at the time points specified in Section 8.1 to compare BMC and body composition before and after study treatment. For the DXA scan, at least 2 vertebrae are required (i.e. L3-L4) and the same 2 vertebrae must be included on all follow-up exams.

If results from the DXA image suggest a compression fracture, the study PI or coordinator will confirm that the participant's primary care team knows of the results and appropriate follow-up (i.e. lumbar spine x-ray) is done. Note that there is no need to repeat an x-ray if (1) one was performed within the previous 12 months for the evaluation of the same vertebra with the highest BMD Z-score, and (2) was negative for fracture.

For subjects enrolled at the UMN, pQCT of the left tibia and non-dominant radius

will also be performed at the time points specified in Section 8.1.

### **8.2.5 Diet and Activity Questionnaire**

A food frequency questionnaire (FFQ) to determine dietary calcium intake (Appendix II) and a physical activity questionnaire (Appendix III) will be completed by the subjects or their parent(s)/legal guardian(s) at the time points described in section 8.1.

If a subject is unable to return to the clinical site for Day 180 and/or Day 270 study visits, the study coordinator will send the questionnaires to the participant and/or parent/guardian with the intent to complete them via telephone at a pre-arranged time.

### **8.2.6 Unscheduled Visits**

Additional visits will be scheduled as needed throughout the study period to address concerning signs or symptoms reported by subjects.

## **8.3 Laboratory Testing Procedures**

During the study, creatinine, total calcium, Vitamin D (D2+D3), and intact parathyroid hormone (iPTH) will be analyzed to monitor subject safety.

Additionally, levels of markers of bone formation (OCN and P1NP) and resorption (CTX and DPD), cytokines (IL-6, IL-7, and TNF- $\alpha$ ), RANKL, and OPG will be analyzed in batches or at the end of the study.

### **8.3.1 Laboratory Testing Procedures**

Specimens for analysis of safety parameters, markers of bone turnover, cytokines, RANKL, and OPG will be collected as described in Table below at the time points indicated in section 8.1. Venipuncture or blood collection from a venous catheter (if the patient has one in place) will be performed by trained certified nursing assistants, nurses, nurse practitioners, or physicians and collection tubes will be handled per the manufacturer's recommendations.

#### **Laboratory Analytes and Collection Information**

Analyte	Matrix	Tube Type	Volume
Carboxy terminal collagen crosslinks (CTX) a	Plasma	K 2 EDTA (di-potassium ethylenediaminetetraacetic acid; purple-top tube)	3 mL blood (minimum 700 $\mu$ l plasma)
Procollagen type 1 amino terminal propeptide (P1NP) a	Plasma	K 2 EDTA (purple-top tube)	
Osteocalcin (OCN) a	Plasma	K 2 EDTA (purple-top tube)	
Receptor activator of nuclear factor- $\kappa$ B ligand (RANKL) a	Plasma	K 2 EDTA (purple-top tube)	
Osteoprogenin (OPG) a	Plasma	K 2 EDTA (purple-top tube)	

Analyte	Matrix	Tube Type	Volume
Interleukin (IL)-6 b	Plasma	K 2 EDTA (purple-top tube)	3 mL blood (minimum 700 µl plasma)
IL-7 b	Plasma	K 2 EDTA (purple-top tube)	
Tumor necrosis factor alpha (TNF- $\alpha$ ) b	Plasma	K 2 EDTA (purple-top tube)	
Intact parathyroid hormone (iPTH)	Plasma	K 2 EDTA (purple-top tube)	1 mL blood (minimum 300 µl plasma)
Urinary deoxypyridinoline (DPD) d	Urine	Urine specimen container	1 mL
Urine Creatinine d	Urine	Urine specimen container	

a Single sample for CTX, P1NP, OCN, RANKL, and OPG analysis collected in the same tube.  
b Single sample for IL-6, IL-7, and TNF- $\alpha$  analysis collected in the same tube.  
c Single sample for total calcium, vitamin D (D2+D3), and creatinine analysis collected in the same tube.  
d Single sample for DPD and creatinine collected in the same container.

### 8.3.2 Specimen Processing and Storage

Research samples collected for the purpose of this study will be processed and stored frozen until the time of batch testing at the University of Minnesota, unless otherwise specified below. Upon completion of batch testing and verification of results at the University of Minnesota, any remaining samples will be destroyed.

#### Vitamin D (D2+D3), Total Calcium, and Creatinine:

This testing will be done by the institutional lab with the results recorded in OnCore for the purposes of this study. Vitamin D will be measured by mass spectrometry.

#### PTH, intact

This testing will be done by the institutional lab with the results recorded in OnCore for the purposes of this study.

#### Plasma samples (CTX, P1NP, OCN, RANKL, OPG, IL-6, IL-7, and TNF- $\alpha$ ):

Collect blood in 2 purple-top (ethylenediaminetetraacetic acid [EDTA]) tubes (3 mL each).

Refer to the Affiliate Lab Manual for sample processing and storage instructions.

#### Urine sample for DPD and Urine Creatinine:

Collect at least 1 mL of urine in a preservative-free urine specimen container. A morning collection is preferred, but not mandatory. The time of the urine collection must be recorded. Collect urine mid-stream, voided directly into a sterile container (if possible). Avoid prolonged exposure to light, especially sunlight. During routine processing, samples are not affected by normal, artificial laboratory lighting.

Refer to the Affiliate Lab Manual for sample processing and storage instructions.

**End of Pamidronate Infusion Serum Calcium:**

A serum calcium level will be done after the pamidronate infusion end and prior to discharge from clinic on the day of the pamidronate per section 7.3.1.

**Post Pamidronate Spot Urine for Albumin and Creatinine and Serum Creatinine:**

Ideally the morning after each pamidronate infusion, the participant will return to the study center for a routine serum creatinine and a spot urine for albumin and creatinine to calculate albumin to creatinine ratio. A morning collection is preferred, but not mandatory. The time of the urine collection must be recorded. The samples will be processed in the site's clinical laboratory but charged to research.

If the participant is unable or unwilling to return to the study center the morning after the pamidronate infusion, the samples may be collected within 7 days after the infusion. A morning collection is preferred, but not mandatory. The time of the urine collection must be recorded. Arrangements for the testing will be done on a per patient basis (i.e. at the study center on a different day or at an outside facility).

**8.3.3 Specimen Processing and Storage - University of Minnesota**

Fairview Acute Care Lab will process and store frozen (within 30-60 minutes of processing) per the study lab slips all research samples until the time of batch transfer to the Cytokine Lab ([name]) for analysis.

**8.3.4 Specimen Shipping – Fred Hutchinson Cancer Research Center**

Samples collected at Fred Hutchinson Cancer Research Center will be processed at a local laboratory as detailed in the affiliate manual, then frozen in aliquots for CTX, P1NP, OCN, RANKL, OPG, IL-6, IL-7, TNF- $\alpha$ , and urinary DPD and creatinine and stored at frozen until the time of batch shipping to the UMN.

The samples are to be shipped Monday through Thursday only on dry ice in a Styrofoam container inside a cardboard sleeve. Send the samples via FedEx Priority Overnight to the address below:

[name] Laboratory  
Cytokine Lab  
[name]  
[name]  
[name]  
[contact]

### 8.3.5 Laboratory Testing: Normal Values

Reference ranges for standard analytes are presented in section 8.3.1.

#### Laboratory Reference Ranges

	University of Minnesota (UMN)		Fred Hutchinson Cancer		
Creatinine (mg/dL)	0-21d	0.33-1.01	2 months-2 years	0.1-0.4	
	22 days-8 years	0.15-0.53			
	9-14 years	0.39-0.73		0.1-0.6	
	15-19y	0.5-1.0		0.2-0.9	
	20 y and older, F	0.52-1.04		0.2-1.1	
Calcium ("corrected calcium"?)	20 y and older, M	0.66-1.25	≥14 years	8.7-10.7	
	Age	mg/dL			
	0-11 mo	8.5-10.7			
	1-18 yr	9.1-10.3			
	19 yr & older	8.5-10.1			
Ionized Calcium	Age	mg/dL			
	0-11 mo	5.1-6.3			
	1 yr and older	4.4-5.2			
Vit D (D2 + D3) / 25-hydroxy (OH) vitamin D (ng/mL)	20-75		30-100		
Intact parathyroid hormone (iPTH) (pg/mL)	12-72pg/mL		12-75		
Interleukin (IL)-6 (pg/mL)	≤3.0		≤3.0		
IL-7 (pg/mL)	0.66-9.2		0.66-9.2		
Tumor necrosis factor alpha (TNF- $\alpha$ ) (pg/mL)	≤8.8		≤8.8		

a IL-6, IL-7, and TNF- $\alpha$  samples from Fred Hutchinson Cancer Research Center will be analyzed at UMN.

Laboratory normal ranges for CTX, DPD, P1NP, OCN, RANKL, and OPG vary with age. Urinary DPD will be adjusted for urinary creatinine content.

If total calcium or vitamin D (D2+D3)/25-OH vitamin D is below the normal range, supplementation will be administered per Section 7.3.

If creatinine level for a subject randomized to receive pamidronate becomes elevated during the study (creatinine level  $>2$  times the baseline value at Study Entry) refer to section 7.3.2 for treatment modification and monitoring.

## **9 Event Monitoring, Documentation and Reporting**

Toxicity and adverse events will be classified according to NCI's Common Terminology Criteria for Adverse Events V 4.0 (CTCAE). A copy of the CTCAE can be downloaded from the CTEP home page

[http://ctep.cancer.gov/protocolDevelopment/electronic\\_applications/ctc.htm#ctc\\_40](http://ctep.cancer.gov/protocolDevelopment/electronic_applications/ctc.htm#ctc_40)

### **9.1 Definitions**

The following definitions are based on the Code of Federal Regulations Title 21 Part 312.32 (21CFR312.32(a)).

**Adverse Event:** Any untoward medical occurrence associated with the use of a drug in humans, whether or not considered drug related.

**Suspected Adverse Reaction:** Any adverse event for which there is a reasonable possibility that the drug caused the adverse event.

**Treatment-Emergent Adverse Event:** Any event not present prior to the initiation of the treatment or any event already present that worsens in either intensity or frequency following exposure to the treatment. A treatment emergent AE refers to an event temporally related to the study treatment regardless of the causality assessment by the investigator.

**Life-Threatening Adverse Event Or Life-Threatening Suspected Adverse Reaction:** An adverse event or suspected adverse reaction is considered "life-threatening" if, in the view of either the investigator or sponsor, its occurrence places the patient or subject at immediate risk of death.

**Serious Adverse Event Or Serious Suspected Adverse Reaction:** An adverse event or suspected adverse reaction is considered "serious" if, in the view of either the investigator or sponsor, it results in any of the following outcomes:

- Death
- A life-threatening adverse event
- Inpatient hospitalization or prolongation of existing hospitalization
- A persistent or significant incapacity or substantial disruption of the ability to conduct normal life functions
- A congenital anomaly/birth defect.

Important medical events that may not result in death, be life-threatening, or require hospitalization may be considered serious when, based upon appropriate medical judgment, they may jeopardize the patient or subject and may require medical or surgical intervention to prevent one of the outcomes listed in this definition.

If either the IND sponsor or the investigator believes the event is life-threatening or serious, the event must be evaluated by the sponsor for expedited reporting (21CRF 312.32(a)).

**Event Attribution Categories:**

CTCAE does not define an AE as necessarily ‘caused by a therapeutic intervention. The clinical investigator must assign attribution for an adverse event after naming and grading of the event.

Attribution	Description
Unrelated	The AE is clearly NOT related to the intervention
Unlikely	The AE is doubtfully related to the intervention
Possible	The AE may be related to the intervention
Probable	The AE is likely related to the intervention
Definite	The AE is clearly related to the intervention

**Unexpected adverse event or unexpected suspected adverse reaction:** An adverse event or suspected adverse reaction is considered “unexpected” if it is not listed in the investigator brochure or is not listed at the specificity or severity that has been observed; or, if an investigator brochure is not required or available, is not consistent with the risk information described in the general investigational plan or elsewhere in the current application, as amended. Thus, adverse events that occur as part of the transplant or underlying disease are considered unexpected; however, they will not be reportable per section 9.4.

**Expedited (Rapid) Reporting:** Certain events may require rapid notification to entities providing patient safety oversight (e.g. IRB, FDA) as detailed in section 9.4.

## 9.2 Documentation of Adverse Events

The goal of AE monitoring will be to focus on events that are related directly to study participation, not the transplant procedure or the disease under treatment unless study participation exacerbates the event. Due to the complex medical condition of the post-transplant patient, monitoring for adverse events will focus on events beginning with the 1st dose of pamidronate through the Day 360 visit.

For patients assigned to pamidronate, a toxicity assessment will be done in conjunction with each infusion (Day 90, 180, and 270) at the following time points:

- Prior to the pamidronate infusion - within 72 hours before the infusion
- 1 week (+/- 3 days) after each pamidronate infusion via telephone interview
- At any unplanned visit

At each of these time points the worst grade of the targeted toxicity since the previous assessment will be recorded in addition to any unexpected toxicities felt at least possibly related to pamidronate.

Of special concern are rare, but potentially serious risks associated with pamidronate which, if serious enough will lead to the discontinuation of the study drug per section 12.5. These targeted toxicities (based on CTCAE v4) will be collected on all patients (control and pamidronate) are:

- Anterior uveitis by subject's report (blurred vision, eye pain, redness, sensitivity to light, irregular pupil)
- Atrial fibrillation by the subject's report (palpitations, chest pain, shortness of breath)
- Osteonecrosis of the jaw by subject's report (jaw pain, swelling, redness, or other signs of infection in the gums, gums or sockets that don't heal after dental work, numbness or a heavy feeling in the jaw, draining of pus, visible bone in the mouth, roughness of the gums in a particular area) and/or physical examination at study visits.

All targeted toxicities, regardless of grade, and other events, grade 3 or greater that are felt at least possibly related to study treatment or cannot be explained by another cause (i.e. unexpected, not related to transplant, disease for which the transplant was done, underlying medical condition, etc.) will be recorded in OnCore for all patients.

After completion of the targeted toxicity form at day 360 formal collection of adverse events ends; however the sponsor/investigator must report upon knowledge any treatment related event meeting the expedited reporting criteria found in section 9.1 regardless of timing to pamidronate.

From signing of consent through the Day 360 visit any unexpected adverse event that is felt to be at least possibly related to the vitamin D and calcium and/or study procedures (research specimen collection, DXA) will be recorded in the study's case report forms.

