#### **7.4.3 Expected Toxicities**

The most common side effects in adults receiving pamidronate are hypertension, injection site reaction, hypocalcemia, hypokalemia, hypomagnesemia, hypophosphatemia, loss of appetite, nausea, vomiting, anemia, urinary tract infectious disease, cough, dyspnea, fatigue, and malaise. Other serious adverse effects that have been observed in adults are arthralgia, aseptic necrosis of bone of jaw, bone pain, myalgia, seizure, deteriorating renal function, focal segmental glomerulosclerosis, and nephrotoxicity.

In studies of pamidronate in children, hypocalcemia is also a common side effect. Brief acute phase reactions, including fever, headache, nausea, vomiting, rash, tachycardia, myalgia, and bone pain have also been noted on first exposure in pediatric patients. Uncommon side effects are nephrotoxicity, anterior uveitis, and atrial fibrillation. Due to these possible side effects, subjects will have laboratory evaluations performed to monitor for hypocalcemia or nephrotoxicity. Furthermore, any safety issue that might arise will be quickly recognized and treated as these subjects will be undergoing intensive monitoring following HCT.

Potential long-term side effects are radiographic metaphyseal bands, iatrogenic osteopetrosis, fractures after discontinuation of drug in growing children, delayed healing at osteotomy sites, esophageal cancer, and osteonecrosis of the jaw.

Long-term side effects are unlikely after a short-term treatment with pamidronate in patients without an underlying metabolic bone disease. There have been no reports of either esophageal cancer or osteonecrosis of the jaw in children after treatment with pamidronate.

Refer to the prescribing information for additional information.

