## **12.5 Early Study Stopping Rule For Excessive Toxicity**

Any grade 4 or 5 study-related toxicity in pamidronate-treated participants will result in a pause in study randomization for a re-evaluation of the treatment plan.

In addition to the foregoing, three toxicities will be monitored in participants in both the pamidronate and control groups: uveitis, atrial fibrillation, and osteonecrosis of the jaw (ONJ) of grade 3 or higher (as these toxicities will be recorded only if they are of grade 3 or higher). These toxicities will be monitored at interim analyses by comparing the two groups using a Lan-DeMets stopping rule with an O'Brien-Fleming alpha-spending function. For this monitoring purpose,

the outcome for each participant will be the count of AEs of any of these three types, and the P-value for comparing the groups will be computed using a permutation test that permutes groups labels on participants, with test statistic the difference between groups in their average numbers of AEs. Interim analyses will be performed every 6 months.

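### Hypocalcemia and kidney toxicity reach the adverse-event record through a filter that acts unequally by arm, and no analysis is planned of the scheduled calcium and creatinine values that could compare the arms

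*Combined protocol and SAP*

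**What the plan says.** **Which harms are expected.** Section 7.4.3 states: "In studies of pamidronate in children, hypocalcemia is also a common side effect". It lists nephrotoxicity among the uncommon effects and says that "subjects will have laboratory evaluations performed to monitor for hypocalcemia or nephrotoxicity".

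**What is recorded as an adverse event.** Section 9.2 introduces its list with "These targeted toxicities (based on CTCAE v4) will be collected on all patients (control and pamidronate) are". The list has three entries: anterior uveitis, atrial fibrillation and osteonecrosis of the jaw, recorded at any grade. Anything else is recorded only if it belongs to "other events, grade 3 or greater that are felt at least possibly related to study treatment or cannot be explained by another cause". Section 9.2 names transplant, the disease being transplanted and underlying medical conditions as examples of other causes. At the infusion-linked assessments, which only pamidronate patients have, the targeted toxicities are recorded "in addition to any unexpected toxicities felt at least possibly related to pamidronate".

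**What is measured.** Section 8.2.2 says: "At the time points described in Section 8.1, blood will be collected for analysis of creatinine, ionized or corrected calcium". The Section 8.1 schedule marks creatinine and calcium at Days 90, 180 and 270 with no restriction by arm, and neither at Day 360. For vitamin D, total calcium and creatinine, Section 8.3.2 says: "This testing will be done by the institutional lab with the results recorded in OnCore for the purposes of this study". End-of-infusion calcium and post-infusion creatinine and urine albumin are footnoted in Section 8.1 as applying to pamidronate patients only.

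**What is compared.** In Section 12.5, "three toxicities will be monitored in participants in both the pamidronate and control groups: uveitis, atrial fibrillation, and osteonecrosis of the jaw", at interim analyses every 6 months. Section 12.4 plans no analysis of calcium, creatinine or urine albumin.

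**The concern.** The two harms for which the laboratory monitoring exists have no planned controlled summary. Their adverse-event counts depend on a judgment made by someone who knows the arm. On pamidronate, a grade 3 creatinine rise can readily be called possibly related. On control, the same rise has no pamidronate to be related to, and after a transplant another explanation is usually at hand, so it can go unrecorded. A difference between arms in these counts would mix any drug effect with the effect of the recording rule.

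The scheduled laboratory values avoid that judgment, but with no pre-specified analysis they may go unused, or be summarized in a way that favors one arm. What is at stake is whether the Data and Safety Monitoring Council and the final report can say anything controlled about the most foreseeable harms. The primary endpoint is not affected.

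**Working it through.** The plan states no figure on this point, so there is none to reproduce. The check follows the routes by which these harms can be captured, then counts draws.

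**1. Adverse-event routes.**
- Targeted list (9.2): neither harm is on it.
- Other events (9.2): grade 3 or higher, and either at least possibly related or not otherwise explained. The second branch is open to controls, but post-transplant causes can close it.
- Infusion-linked assessments (9.2): pamidronate patients only and, beyond the targeted list, for unexpected toxicities. Section 7.4.3 lists hypocalcemia and nephrotoxicity as known effects.
- Events related to vitamin D, calcium or study procedures (9.2): unexpected events only.

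No route takes both harms in both arms without a test of grade and cause.

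**2. Laboratory route.** From Sections 8.1 and 7.4.1:

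| Draw (calcium or creatinine) | Control | Pamidronate |
|---|---|---|
| Day 90, before the first infusion | yes | yes |
| After infusions 1, 2 and 3 | no | 3 draws |
| Days 180 and 270 (pre-infusion on pamidronate) | 2 draws | 2 draws |
| Day 360 | none | none |

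Section 7.4.1 requires the Day 90 samples to be taken before the infusion, so Day 90 is a baseline. The common later draws are Days 180 and 270, each about three months after the previous infusion. No common draw follows the third infusion. Section 8.2.1 lets control patients replace non-routine visits by telephone, and Section 8.1.3 says Day 270 is not standard follow-up, so control values may be missing.

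**3. What an unplanned count over all draws would show.** After the first infusion, k = 2 draws on control and k = 2 + 3 = 5 on pamidronate. The documents give no abnormality rate. Assume the same chance p per draw in both arms, independent between draws, and no drug effect. Then P(at least one abnormal value) = 1 − (1 − p)^k.

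| Assumed p | Control, k = 2 | Pamidronate, k = 5 | Ratio |
|---|---|---|---|
| 2% | 1 − 0.98² = 4.0% | 1 − 0.98⁵ = 9.6% | 2.4 |
| 5% | 1 − 0.95² = 9.8% | 1 − 0.95⁵ = 22.6% | 2.3 |
| 10% | 1 − 0.90² = 19.0% | 1 − 0.90⁵ = 41.0% | 2.2 |

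Positive correlation between a patient's draws would narrow the gap. The protocol does not plan such a count; the table shows why the rule should be fixed in advance.

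**4. Size of the usable comparison.** Section 12.1 projects 86 patients at Days 90, 180 and 270, or 86 / 2 = 43 per arm. That is a ceiling, because the same section allows for deaths and drop-out after Day 90.

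**The case against.** The strongest reply is that the monitoring promised in Section 7.4.3 is delivered, and that a between-arm test was never promised. Calcium is checked before and after each infusion, and creatinine and urine albumin after it. Creatinine governs holding and discontinuation. Under Section 12.5, any grade 4 or 5 study-related toxicity on pamidronate pauses randomization, and that covers both harms. Section 9.4 has the affiliate report serious events regardless of attribution. Section 10.4 has the Council review progress at least quarterly. Section 9.2 also gives a reason for focused collection: the medical complexity of these patients.

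All of this stands as protection of individual patients. None of it yields an unfiltered by-arm summary. The pause rule is single-arm and depends on attribution, and the serious-event rule covers only serious events.

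A reader might infer from Section 9.2 that the arms cannot be compared at all on these harms, or that grade 1 and 2 events are lost. The documents do not support either. Calcium and creatinine are scheduled in both arms, and the results go into OnCore with no grade or attribution condition, so low-grade laboratory abnormalities can still be graded later. Nor can it be said that the control count must fall to zero, since an unexplained grade 3 event on control is recordable.

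It is also fair to object that the Day 180 and Day 270 values say little about acute post-infusion effects. That limit remains under any fix that adds no samples.

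**Conclusion.** The point holds for the adverse-event record and for the missing analysis. Counts of hypocalcemia and kidney toxicity under Section 9.2 pass a test of grade and cause that differs by arm in an open-label trial, so they should not be read as a treatment comparison. The scheduled Day 180 and Day 270 calcium and creatinine values allow a limited comparison, with at most about 43 patients per arm, and no analysis of them is planned.

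The size of the attribution bias cannot be computed from the documents. The size of the sampling bias in a count over all draws can only be illustrated: a ratio of 2.2 to 2.4 with no true effect, for assumed rates of 2% to 10% per draw, equal in both arms and independent between draws.

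**What to change.** **Section 9.2.** Record hypocalcemia and creatinine increase in both arms regardless of grade or attribution, by grading the scheduled calcium and creatinine values by CTCAE. State which calcium measure is graded: Sections 8.1 and 8.2.2 schedule ionized or corrected calcium, whereas the OnCore statement in Section 8.3.2 names total calcium.

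**Sections 12.4 and 12.5.** Pre-specify a by-arm summary at Days 180 and 270, with Day 90 as baseline and the number of patients with a value shown for each arm and visit. Give it to the Council with the 6-monthly interim analyses. At this sample size it should be descriptive and kept apart from the three-event stopping test.

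**Post-infusion results.** Report end-of-infusion calcium and post-infusion creatinine and urine albumin separately, labeled as single-arm data, and do not pool them with the scheduled draws.

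**Cost.** Two lines on the toxicity form and some programming; no new samples and no change to clinical management. There will be more low-grade events to list. Acute post-infusion effects, and any effect after the third infusion, remain without a control.
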